## **7. DEVICE**

Details about the description, operation, preparation and use of the Renew™ NCP-5 device are found in a separate Training Manual.

### **7.1 Device Description**

The Renew™ NCP-5 device used in the study has been FDA cleared under K152115. The Renew™ NCP-5 device has the following major components: a switch panel, a foldable treatment bed, main unit, and a set of patient cuffs. During Renew™ NCP-5 treatments, the patient's lower extremities are wrapped in compressive pneumatic cuffs applied to the calves, lower thighs, and buttocks. The device is a microprocessor-controlled system that sequentially inflates then deflates three pairs of air cuffs, which compress vascular beds in the muscles of the calves, thighs, and buttocks in synchrony with the heart cycle to achieve the desired therapy. The attached computer provides real time monitoring of: heart rate; Inflation and deflation time; treatment time; treatment pressure; and peak diastolic/peak systolic ratio (P/P). The PC provides synchronous display of the ECG signal, the inflation/deflation signal, and the pulse wave (Renew Group Private, Ltd., 2017).

Input and data from the ECG, plethysmograph, and the pressure/vacuum transducers are processed by the microprocessor to control the valve timing and air pressure in the tank that is delivered to the cuffs. Treatment pressure is monitored with an internal pressure sensor and the operator-selected set point maintained by a closed-loop control system. Valve inflation and deflation timing is also set by the operator based on the relative position of the R-wave of the patient's ECG. Detailed description of the device is also shown in Appendix D, the Investigator Brochure.

---

## 7.2 Acquisition of Device

The Renew™ NCP-5 system arrives in a wooden crate as a single shipment consisting of: NCP-5 unit, Laptop PC, and Accessories (cables, hoses, supplies). The unit is also the patient treatment platform. Delivery includes factory installation and set-up. Before the technician departs from the installation site, s/he completes a checklist and the site manager signs confirmation of the quality control/assurance steps taken by the technician.

## 7.3 Storage and Stability

The Renew™ NCP-5 system should be stored at room temperature in a secure location. It does not require calibration and can be serviced by an approved technician, as needed.

## 7.4 Preparation

The technicians will follow the preparation and treatment instructions as outlined in the Renew™ NCP-5 training manual.

## 7.5 Dosing and Administration

The subject is positioned lying flat on the foldable treatment bed and pneumatic, blood pressure like cuffs, are placed on his/her legs: calf, lower thigh and buttocks. They are connected to monitors that record heart rate and rhythm. The cuffs will be inflated and deflated based on the actions of the subject's heart (between heartbeats). Compression pressure will be given at different levels depending on whether the subject is assigned to the treatment group or the active sham group. The subject's overall ability to tolerate the treatment may impact the pressure applied. The operator of the device will increase pressure progressively and assess the subject's level of discomfort.

For all treatment subjects, the first four sessions represent the escalation phase. There will be a 5-minute ramp up period where the pressure is increased 1PSI / min until the desired pressure is reached. The goal for the treatment group will be at least 2.5 PSI (pounds per square inch) for the first treatment, and then escalate the pressure gradually through the fourth session at which time the goal for the subject should be at least an average of 3 PSI/session. For all sessions, the subject should reach the highest tolerable pressure. Patients are not to be terminated if they can't reach 3-6 PSI. Each treatment session is 60 minutes however, if necessary, on an as-needed basis, a treatment session of 30 minutes or more ( $\geq 30$  minutes) will be considered as a completed session.

After the fourth session, the operator shall continue to slowly increase the pressure to give the subject time to adapt to the rising pressure in order to reach the maximum level that the subject finds comfortable with a goal of reaching 3-6 PSI or the highest tolerable pressure. The operator may alter the pressure in the event that a subject becomes uncomfortable after the start of treatment. For both treatment arms, the Renew™ NCP-5 operator should record the average compression pressure and

---

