#### Confidentiality Statement

---

The confidential information in this document is provided to you as an investigator or consultant for review by you, your staff, and the applicable Institutional Review Board. Your acceptance of this document constitutes agreement that you will not disclose the information contained herein to others without written authorization from the sponsor.

The secondary effectiveness endpoints of the study include:

- The safety of Renew™ NCP-5 treatments as reflected in adverse events, labs and vital signs;
- The average of the change from baseline in Alzheimer’s Disease Cooperative Study-Activities of Daily Living (**ADCS-ADL**) Total Score at 12, 18 and 24 weeks after initiation of treatment;
- The answers to the NIA’s Disease Cooperative Study-Clinical Global Impression of Change Scale (**ADCS-CGIC**) at 12, 18 and 24 weeks after initiation of treatment;
- The average of the change from baseline in executive function, assessed by the **Trail Making Test B** at 12, 18 and 24 weeks after initiation of treatment;
- The average of the change from baseline in **ADAS-Cog14** at 12, 18 and 24 weeks after initiation of treatment. ADAS-Cog14 score will be calculated using the subtests from the vADAS-Cog test and will not be conducted as a separate test.

Sponsor will repeat the analysis and conduct the battery of secondary endpoints on the 9 and 12 month data.

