### Confidentiality Statement

---

The confidential information in this document is provided to you as an investigator or consultant for review by you, your staff, and the applicable Institutional Review Board. Your acceptance of this document constitutes agreement that you will not disclose the information contained herein to others without written authorization from the sponsor.

maximum diastolic augmentation (the ratio of diastolic peak height to systolic peak height – P/P) during each treatment session just before (1-2 minutes) reducing the pressure at the end of treatment.

Active sham control subjects will receive the same initial and maintenance treatment regimens as treated subjects except that the pressure will not exceed an average of 0.5 PSI over all treatments. Active sham subjects will undergo cognitive testing and imaging at the same time points as treated subjects. The purpose of the active sham Renew™ NCP-5 treatments is to give the subject an experience that seems to be an authentic treatment but, instead, provides minimal or no therapeutic benefit.

For a active sham treatment, the subject is handled exactly as in a typical therapeutic treatment (vitals, wrapping of cuffs, etc.), but with two important differences:

- The treatment pressure is set to a maximum of 0.5 psi and is kept there for the duration of the active sham treatment. Note that it may be difficult to maintain the pressure at exactly 0.5 psi. Although all attempts should be made to use a maximum of 0.5 psi, occasional, transient excursions as high as 1.0 psi are permissible.
- Although the subject will have ECG electrodes attached to his/her chest as per usual Renew™ NCP-5 protocol, the cable from those leads will not be connected to the Renew™ NCP-5 machine. Instead, the Renew™ NCP-5 machine will be connected to an ECG simulator hidden under the plastic “skirt” of the machine.

The ECG simulator is used to drive the Renew™ NCP-5 machine, rather than the subject’s actual ECG. This causes the "squeezes" applied by the machine to be out of sync with the patient’s heartbeat, thus minimizing any possible therapeutic effect.

ECG simulator settings are as follows:

- Normal sinus rhythm (NSR)
- Heart rate = 70 bpm
- Amplitude – 4 mV
- Sleep – No

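### Pressure is titrated to the subject's tolerance in the treated arm only, and no arm-neutral discomfort question is fixed, so mild in-session events may be elicited unequally

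*Protocol*

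**What the plan says.** Protocol Section 7.5 opens with a paragraph that covers both groups and contains the instruction "The operator of the device will increase pressure progressively and assess the subject's level of discomfort". It then turns to one arm: "For all treatment subjects, the first four sessions represent the escalation phase". That paragraph describes a start-up ramp, goals for the first four sessions, and the aim of the highest tolerable pressure in every session. After session four the operator goes on raising pressure slowly, "in order to reach the maximum level that the subject finds comfortable with a goal of reaching 3-6 PSI or the highest tolerable pressure", and "The operator may alter the pressure in the event that a subject becomes uncomfortable after the start of treatment". Sections 6.4, 8.4.3 and 8.4.4 repeat the escalation for treatment subjects only.

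For sham, the same section says "The treatment pressure is set to a maximum of 0.5 psi and is kept there for the duration of the active sham treatment", with brief excursions allowed. It adds that "Active sham control subjects will receive the same initial and maintenance treatment regimens as treated subjects", apart from pressure, and that "the subject is handled exactly as in a typical therapeutic treatment (vitals, wrapping of cuffs, etc.), but with two important differences". The two differences listed are the pressure and the ECG source.

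Section 5.2.2 lists among the secondary endpoints "The safety of Renew™ NCP-5 treatments as reflected in adverse events, labs and vital signs". Section 9.4 blinds the subject and the psychometrician but not the device operator or the principal investigator. Section 9.2 leaves the first assessment of adverse events to the investigator or a medically qualified designee, and relatedness to the investigator.

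**The concern.** An operator cannot find the highest pressure a subject tolerates without feedback from that subject. The treated arm therefore has a built-in reason for talk about discomfort, which a session at constant pressure lacks. If some of that talk ends up as recorded adverse events, the between-arm difference mixes device harm with unequal elicitation, and the two cannot be separated afterwards. The same talk may also act as a cue in a subject-blinded trial, where the sham session is meant to pass for a real one. The statement that sham handling differs in only two respects hides this, because the ramp, the escalation and the exchange that goes with them are written for treated subjects only.

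**Working it through.** The protocol states no figure for adverse event ascertainment, so there is none to reproduce. The check sets the provisions side by side, counts the scheduled enquiries, and then shows how wide the unknown is.

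**1. Provisions by arm**

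| Element | Treated | Sham | Where |
|---|---|---|---|
| Ramp and four-session escalation | Specified | Not specified | 7.5, 6.4, 8.4.3, 8.4.4 |
| Raising pressure to the highest tolerable level | Specified, all sessions | Pressure set and held | 7.5 |
| General instruction to assess discomfort | Applies | Not excluded, but tied to increasing pressure | 7.5, opening paragraph |
| Number of sessions | Same regimen | Same regimen | 7.5 |
| Adverse event collection | Every visit | Every visit | 5.1, Table 2, 8.4.3 to 8.4.10 |
| Scripted discomfort question | None fixed | None fixed | 7.5 |

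**2. Scheduled enquiries.** Each subject has 35 initial sessions, then 2 per week to week 24. If the initial period lasts w weeks, with w from 7 to 12 (Sections 5.1 and 7.6), sessions = 35 + 2 × (24 − w).
- w = 7: 35 + 2 × 17 = 69
- w = 12: 35 + 2 × 12 = 59

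These counts hold in both arms, and adverse events are collected throughout. The ratio of scheduled enquiries is 1:1. Any excess in the treated arm can come only from unscripted talk during titration, which the protocol does not quantify.

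**3. Which events are exposed.** Section 3.1 lists skin irritation, abrasions and bruising, headache, leg and low back pain, edema, toothache and fatigue. A question about whether a pressure is comfortable bears mainly on leg or back pain during inflation. Skin changes and edema can be seen when the cuffs are handled, which happens in both arms.

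**4. Range of the unknown (illustration; all rates assumed).** Let the true event rate p be equal in both arms, with detection d_S in sham and d_T in treated. Recorded rates are a = p × d_S and b = p × d_T. With n = 50 or 125 per arm (100 to 250 subjects, 1:1) and two-sided 0.05, the chance of a nominally significant excess in the treated arm is Φ[(b − a − 1.96·SE0)/SE1]. Here SE0 = √[2m(1 − m)/n] with m = (a + b)/2, and SE1 = √{[a(1 − a) + b(1 − b)]/n}.

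Worked case: p = 20%, detection 60% and 90%, n = 50. Then a = 0.12, b = 0.18, m = 0.15, SE0 = 0.0714, SE1 = 0.0712, and (0.06 − 0.1400)/0.0712 = −1.12, which gives 13.1%.

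| Detection, sham / treated | Recorded rates, p = 20% | Recorded rates, p = 40% | Chance, n = 50 (p = 20%, 40%) | Chance, n = 125 (p = 20%, 40%) |
|---|---|---|---|---|
| 80% / 90% | 16%, 18% | 32%, 36% | 4.5%, 6.2% | 6.2%, 9.8% |
| 60% / 90% | 12%, 18% | 24%, 36% | 13.1%, 25.6% | 26.3%, 54.4% |
| 50% / 100% | 10%, 20% | 20%, 40% | 28.6%, 59.0% | 60.1%, 93.7% |

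With equal detection the chance in this one direction is about 2.5%. The protocol gives nothing that would select a row, and equal detection is not ruled out.

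**The case against.** The strongest reply is that the protocol already equalises what counts. Adverse events are collected at every visit in both arms, over the same number of sessions. The discomfort instruction stands before the arms are separated, and sham handling is stated to be otherwise the same. Ramp and escalation are simply how the higher pressure is reached, so they can be read as part of the first listed difference. More events at higher pressure may be a true device effect. Operator wording may also sit in the Training Manual or the Manual of Procedures, which are not at hand. For blinding, the pressure gap itself is a far stronger cue, and a script would not remove it.

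Most of this stands, and it disposes of a stronger reading. A reader might infer that treated subjects are prompted at each of their 59 to 69 sessions while sham subjects are never asked and can only volunteer complaints. The documents do not support that: scheduled enquiry is 1:1, no passage exempts sham from the discomfort assessment, and no passage turns the titration exchange into an adverse event query. Nor can a share of missed sham events be calculated, since every input would be an assumption.

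What the reply does not remove is the asymmetry itself. The discomfort instruction is coupled to increasing pressure, which a constant-pressure session does not do. When and how to ask in sham is therefore left to an operator who knows the assignment.

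**Conclusion.** The point holds as a limited one. Titration to tolerance is written for treated subjects only, staff are unblinded, and the protocol fixes no discomfort enquiry common to both arms. Unequal elicitation of mild in-session events is therefore possible, chiefly for leg or back pain, and would tend to overstate device-related events relative to sham. A modest blinding cue is possible as well. The size cannot be derived from the protocol; the illustration shows only that it could be negligible or large, on assumed event and detection rates. This is a worthwhile, cheap improvement to the secondary safety comparison. It does not show that the adverse event data will be biased.

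**What to change.** In Section 7.5, require the operator to put the same scripted discomfort and adverse event question at the same fixed times in every session in both arms, for example at the end of start-up and shortly before the session closes. Record the answer on the session form. Positive answers go to the investigator or designee for assessment under Section 9.2; they are not counted directly as adverse events.

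Reconcile the sentence listing two differences for sham with the treated-only ramp and escalation text, so that operator–subject interaction is matched between arms. No pressure in either arm changes. If the Training Manual already holds such a script, a cross-reference in Section 7.5 is enough.

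The cost is a short protocol addition, one form field, operator retraining, under a minute per session, and more trivial reports to review.

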### Confidentiality Statement

---

The confidential information in this document is provided to you as an investigator or consultant for review by you, your staff, and the applicable Institutional Review Board. Your acceptance of this document constitutes agreement that you will not disclose the information contained herein to others without written authorization from the sponsor.

maximum diastolic augmentation (the ratio of diastolic peak height to systolic peak height – P/P) during each treatment session just before (1-2 minutes) reducing the pressure at the end of treatment.

Active sham control subjects will receive the same initial and maintenance treatment regimens as treated subjects except that the pressure will not exceed an average of 0.5 PSI over all treatments. Active sham subjects will undergo cognitive testing and imaging at the same time points as treated subjects. The purpose of the active sham Renew™ NCP-5 treatments is to give the subject an experience that seems to be an authentic treatment but, instead, provides minimal or no therapeutic benefit.

For a active sham treatment, the subject is handled exactly as in a typical therapeutic treatment (vitals, wrapping of cuffs, etc.), but with two important differences:

- The treatment pressure is set to a maximum of 0.5 psi and is kept there for the duration of the active sham treatment. Note that it may be difficult to maintain the pressure at exactly 0.5 psi. Although all attempts should be made to use a maximum of 0.5 psi, occasional, transient excursions as high as 1.0 psi are permissible.
- Although the subject will have ECG electrodes attached to his/her chest as per usual Renew™ NCP-5 protocol, the cable from those leads will not be connected to the Renew™ NCP-5 machine. Instead, the Renew™ NCP-5 machine will be connected to an ECG simulator hidden under the plastic “skirt” of the machine.

The ECG simulator is used to drive the Renew™ NCP-5 machine, rather than the subject’s actual ECG. This causes the "squeezes" applied by the machine to be out of sync with the patient’s heartbeat, thus minimizing any possible therapeutic effect.

ECG simulator settings are as follows:

- Normal sinus rhythm (NSR)
- Heart rate = 70 bpm
- Amplitude – 4 mV
- Sleep – No

Each treatment session will last for 60-minutes. During the initial treatment period (~1-12 weeks) subjects should be treated five days per week but at a minimum receive treatments three days per week. A maximum of 35 treatments may be administered in the initial 12-week treatment period. Once the first 35 treatments have been administered, the subjects will start the maintenance period where subjects will receive two treatments per week. For subjects who are unable to complete 5 treatment days per week, the treatments should be spread-out as much as possible. In order to complete 5 treatments per week, it is permissible for those subjects to have 2 treatments per day as long as there are no more than 3 days between treatments. If two treatments are conducted on the same day, subjects will need to wait a minimum of one-hour between treatments. Treatments should be

---

#### Confidentiality Statement

---

The confidential information in this document is provided to you as an investigator or consultant for review by you, your staff, and the applicable Institutional Review Board. Your acceptance of this document constitutes agreement that you will not disclose the information contained herein to others without written authorization from the sponsor.

completed per the above schedule. The schedule may be adjusted due to holidays or extenuating circumstances. If subjects need to miss visits during any particular week, then treatments should be added to the week prior to or after the missed visits. A total of 35 treatments must be completed within the 12-week period. More than 7 days between treatments would be considered a protocol violation.

Once the first 35 treatments have been administered, subjects will start the maintenance period where. During the maintenance period, subjects should be treated two days per week, one session per day with a minimum of two full days between each treatment. Subjects may be rescheduled on an as needed basis as long as 6 treatments are maintained within 3-week period. Rescheduling should be kept to a minimum and all efforts should be made to have treatments every week.

Assessment visits should occur the day following the last treatment session but no later than 2 days (48 hours) after the last treatment.

If necessary, on an as-needed basis, a treatment session of 30 minutes or more ( $\geq 30$  minutes) will be considered as a completed session.

Subjects should not eat 60 minutes prior to treatment but if necessary, a light snack is acceptable. Cognitive testing will occur at baseline, weeks 6, 12, 18, 24, 9 and 12 months after baseline. Assessments should be performed the day after the last treatment but no more than 48 hours after the last treatment. For all cognitive testing days, the vADAS-Cog will be administered first and all assessments should be done before 3:00 PM.

If assessment occurs on the same day as treatment, the following must be observed:

- Assessments must occur **after** treatment
- vADAS-Cog must be the first assessment performed
- Assessments must occur **prior** to labs and imaging
- Assessments must be completed before 3:00 PM

## 7.6 Duration of Therapy

Subjects will receive thirty-five 60-minute Renew™ NCP-5 sessions during the 7-to-12-week initial treatment period, and then transition to a lower frequency maintenance period (twice a week) for a total treatment period of 24 weeks.

## 7.7 Tracking of Therapy

The operator uses the PC to enter patient demographics, record pre and post-treatment data, and process data acquired by the microprocessor module to display user feedback for the Renew™ NCP-5 treatment on the LCD showing treatment parameters and patient waveforms during use.

---

## 8. STUDY PROCEDURES AND SCHEDULE

The investigator brochure (IB) will be supplied to sites as a separate document and is attached to this protocol as Appendix D.

### 8.1 Study Specific Procedures

- **Medical and Treatment History** – The subject’s medical and treatment history including past procedures will be obtained by interview and review of medical records. The investigator will review body systems, identify start/stop dates, and determine if the condition is ongoing. Exclusion criteria identify conditions and timeframes that will exclude the subject from participation.
- **Medication history** – Medications and supplements are expected to have been stable for 30 days prior to study start and remain stable over the first 24 weeks of the study for chronic conditions. All medications and supplements will be recorded and their impact on the study will be assessed.
- **Physical examination** – A physical examination, including a brief neurological exam, will be performed to ensure subjects do not exhibit any exclusion criteria and are healthy enough to participate in the study. A second physical exam will take place at end of study.
- **Exercise history and Mobility Assessments** – Subjects will confirm their level of exercise, including cognitive exercises such as language exercises, Sudoku puzzles or online brain training programs (e.g. Lumosity), number of times per week, and length of each exercise session. The aim is to maintain the same level of exercise over the course of the study. Mobility assessments will be performed to assess the participant’s balance, functional mobility, and fall risk.
  - **Timed Up & Go (TUG) Test** – A common clinical screening tool used to assess a patient’s mobility, balance, gait speed, and fall risk. The patient is timed while they rise from an arm chair, walk to a line on the floor three meters away, turn around and walk back to the chair and sit down again. The subject wears his regular footwear and uses his customary walking aid (cane or walker) if necessary.
  - **Functional Reach Test** – A valid and reliable measure used to identify deficits in dynamic balance and fall risk. It is a single-task, dynamic measure of the difference in arm’s length and maximal forward reach using a fixed base of support in the standing position.
- **Patient questionnaire** – Patient self-evaluation questionnaire

---

